#### 9.5 Database management

Data management will be performed by the study team. A data management plan and data control plan have been prepared describing the data management in detail. Appropriate SOP's are also prepared and can be found in the TMF along with the previously mentioned documents. A data handling report will be prepared following database closure.

The data will be stored in a dedicated and secured area at TSD at UIO/OUS with a backup located at an external drive kept locked in the office of the PhD student of the project and not together with the code-list. Data will be stored in a de-identified manner, where each study participant is recognisable by his/her unique trial subject number. The data will be stored until 2035 or later if very long term follow up will be conducted after consultation the Ethics committee at that point in time. The code-list connecting the personal identification of each patient to the study number will be kept on paper in the TMF locked in the investigators office and a digital copy will be made by use of the Nettskjema photo app and stored in tsd. An electronic backup will be made on an IronGuard encrypted memory.

### 10 Statistical methods and data analysis

#### 10.1 Determination of Sample Size

A total of 58 patients will be recruited The number of dropouts is unknown, but the power calculation assumes only 58 randomized patients.

Assuming the time of hospitalization after randomization follows a Weibull distribution with a scale parameter  $\lambda$  = 18 and shape parameter  $\kappa$ =2.2 (corresponding to a median of 15 and an IQR of 10 – 21), we need to include 58 patients (18 in the placebo group, 10 in the 250 mg and 500 mg group and 20 in the 1000 mg group) in order to reach approximately 80% power to show a significant dose-response in this study with a maximal reduction in time of hospitalization of 33%. This calculation is based on optimal designs in dose-finding studies according to the MCPMod methodology with three alternative dose-response curves (linear, e-max and exponential)(Pinheiro, Bornkamp et al. 2014).

#### 10.2 Randomization

#### 10.2.1 Allocation- sequence generation

Key elements to specify regarding allocation of treatment are:

- The department of research support, OUS will generate the allocation sequence
- The allocation ratio in the three phases of the study will be 10:6, 10:6, 20:6 and 20:6
- Block randomization will be used.

#### 10.2.2. Allocation - procedure to randomize a patient

The allocation sequence will be used to pre-package tablets of NR or placebo in separate boxes for each patient for the four phases of the study and to create envelopes for emergency un-blinding. Each patient will receive one pre-packaged box with capsules for the whole study period when the first capsule is taken.

The OUS Department of Research Support will create the randomization list. NR capsules and placebo will hold the new FDA standard; food-good manufacturing practice (GMP) quality. Both will be provided from the largest producer of NR (Chromadex Inc, USA). Since the NR capsules are stable at room temperature and have a long shelf life, we consider distribution through the hospital pharmacy unnecessary and the study staff will distribute the study medication/placebo to the patients through the treating hospital ward or institution. After discharge study medication will be supplied to the patients themselves or necessary arrangements will be made with the home nursing staff where the patient lives. In patients unable to swallow capsules, but with nasogastric access, capsules may be opened and mixed with food/nutrition by the department staff, but not study staff.

#### 10.2.3.Blinding and emergency un-blinding

The patients, department staff, investigators, personnel assessing outcomes and statistician/study staff preparing the data will be blinded to the allocation of patients until the database is locked. For emergency un-blinding see 7.6

#### **10.3 Population for Analysis**

The following populations will be considered for the analyses:

Intention to treat (ITT) population: All randomized participants, regardless of protocol adherence. Per-protocol population (PP): Includes all subjects who have consumed the appropriate dose of NR for more than 30 days (primary population)

Safety population: Includes all subjects who have received at least one dose of study medication. Subjects who withdraw from the study will be included in the safety analysis. A list of withdrawn subjects, with the reasons for withdrawal, will be made.

Primay population: the per-protocol population.

Total number of patients admitted to ICU or the following medical wards: infectious diseases, respiratory medicine, internal medicine or acute medicine during the inclusion period, n

1

- 1. Does not meet inclusion criteria,  $n \rightarrow Stop$ .
- 2. Meet inclusion criteria, n

1

- 1. Exclusion criteria present, n → Stop.
- 2. No exclusion criteria present, n

 $\downarrow$ 

- 1. Not consented to inclusion,  $n \rightarrow Stop$ .
- 2. Consented and included, n

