#### 10.4 Planned analyses

The main statistical analysis is planned when

- The planned number of patients has been included OR the required number and more are included after a period of 2 years.
- All included patients have either finalized their last assessment or has/is withdrawn according to protocol procedures
- All data have been entered, verified and validated according to the data management plan Prior to the main statistical analysis, the data base will be locked for further entering or altering of data. The treatment allocation will be revealed after the database lock and used in the statistical analysis.

Deviation from the original statistical plan will be described and justified in the Clinical Study Report. Amendments to plan can be done until day of DB lock.

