1.1 Background and rationale

Below follows a short summary from "Background and rationale" from study Protocol (B3Short study: shorter recovery time after critical illness. Protocol ID number 2017/1334C. Version number 1.46 dated June 12, 2023, by Oslo University Hospital, Department of Microbiology).

Please see protocol for list of references.

Background

Patients recovering from acute illness often experience prolonged recovery times, influenced by factors such as age, illness duration, and severity. Impaired mitochondrial energy production due to inflammation-induced depletion of nicotinamide adenine dinucleotide (NAD+) may contribute to prolonged recovery phase.

Therapeutic Information

Nicotinamide riboside (NR) is an orally available, safe NAD+ precursor that has been shown to restore NAD+ levels in humans and prolong life in old mice.

Rationale for the Study

Recovery from acute illness is associated with increased risks and delayed or incomplete recovery is common. No "recovery-improvement drug" currently exists. The study aims to administer NR or placebo for 90 days to patients in the recovery phase.

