3.2 Adherence and Protocol Deviations

Adherence to Allocated Treatment

Compliance from inclusion to discharge is defined by administrations recorded in hospital records. Post discharge compliance is determined by self-reported compliance. In addition, results from counting of returned capsules will be reported. Compliance is furthermore assessed based on the percent of subjects who have taken the scheduled number of pills and measurements of NR metabolites that will be available only after unblinding.

Compliance is defined as:

% compliance = (number of days the study drug was taken/ number of days the study medicine was supposed to have been taken.

A patient will be defined as non-compliant if compliance is less than 75% during the hospital stay.

Protocol Deviations

The following are pre-defined major protocol deviations regarded to affect the efficacy of the intervention:

- Entering the trial when the eligibility criteria should have prevented trial entry
- Non-compliance (defined above)
- Diagnosed cancer, or meeting other exclusion criteria, during the treatment period

Protocol deviations are classified prior to unblinding of treatment. The number (and percentage) of patients with major and minor protocol deviations will be summarized by treatment group with details of type of deviation provided. The patients that are included in the Full Analysis Set (see Section 3.4) will be used as the denominator to calculate the percentages. No formal statistical testing will be undertaken.

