3.4 Analysis Populations

The Enrolled set will include all patients who have provided informed consent and have been included into the study data base.

The Full Analysis Set (FAS) will be defined as all patients randomly assigned to a treatment group having received at least one dose of study medication.

The Safety Analysis Set (SAS) will include all patients having received at least one study medication. Subjects who withdraw from the study will be included in the SAS. A list of withdrawn subjects, with the reasons for withdrawal, will be made.

The Per Protocol Analysis Set (PPS) will include all randomised patients meeting the study eligibility criteria, with no major protocol deviations affecting the treatment efficacy, and who are compliant for the study drug.

4 Trial Population

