6.1 Primary Outcome

The primary outcome is length of hospital stay (time to discharge), measured in number of days, and the primary analysis of the primary outcome will be performed on the full analysis set (FAS). A secondary (sensitivity) analysis of the primary outcome will be performed on the per protocol set (PPS).

Statistical Method for Steps 1-3

The comparison of the length of hospital stay between the NR and placebo groups – in each of the three steps – will be carried out with a Weibull survival model, with time as the number of days of hospital stay and treatment (NR vs placebo) as explanatory variable. The estimated treatment effect will be the hazard ratio (HR) for treatment with a 95% confidence interval.

Presentation of Results

The estimated treatment effect (HR) with a 95% confidence interval will be presented, together with the P-value for the null hypothesis of a zero-treatment difference (HR = 1).

The observed mean and standard deviation for placebo and each dose will be presented in a figure, along with the observed values (length of hospital stay) for each individual, as a scatter with connected lines-plot. Figure 1 shows an example with simulated data.

A plot of the Kaplan-Meier survivor function (for time to discharge) of each dose and placebo will be presented.

[figure not shown]

Figure 1: Simulated data

Missing Data

We will have complete data on the length of hospital stay, except for the following situation: A patient dies before being discharged from the hospital. In this case, the patient will be censored at the time of death. Imputation of the length of hospital stay will be performed as a sensitivity analyses (see item 3 below).

Sensitivity Analyses

The following sensitivity analyses will be performed on the primary outcome:

- 1. As described above but on the per protocol set (PPS)
- 2. As described above but with Cox proportional hazard regression instead of Weibull regression
- As described above but with Cox proportional hazard regression and imputation (instead of censoring) of the length of hospital stay with the maximum length of hospital stay (regardless of treatment group) for patients who die before discharge

Subgroup Analyses

There will be no subgroup analyses.

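### Protocol 10.3 makes a per-protocol set (more than 30 days of capsules) the primary population, SAP 6.1 makes it the FAS, and neither document says which prevails

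*Protocol*

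**What the plan says.** Protocol 10.3 lists an ITT set of all randomized participants, a per-protocol set and a safety set. It defines the per-protocol set as "Includes all subjects who have consumed the appropriate dose of NR for more than 30 days (primary population") and closes with "Primay population: the per-protocol population". Protocol 6.3.1 separately says that everyone randomized belongs to the study population.

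SAP 6.1 says that "the primary analysis of the primary outcome will be performed on the full analysis set (FAS"), with the per-protocol set (PPS) as a sensitivity analysis. SAP 3.4 defines the FAS as "all patients randomly assigned to a treatment group having received at least one dose of study medication". Its PPS is not the protocol's set. It takes eligible patients "with no major protocol deviations affecting the treatment efficacy, and who are compliant for the study drug", and SAP 3.2 gives the compliance threshold: "A patient will be defined as non-compliant if compliance is less than 75% during the hospital stay". There is no 30-day requirement.

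On how the two documents relate, Protocol 10.5 leaves details to the SAP and calls its own text an outline. Protocol 10.4 adds "Amendments to plan can be done until day of DB lock" and asks that deviations be described and justified in the Clinical Study Report. SAP 1.1 cites the protocol as "Version number 1.46 dated June 12, 2023" but does not mention that the primary population differs.

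**The concern.** The trial has one primary analysis and two current documents that put it on different sets of patients. If the SAP is followed, the primary result rests on a sound population but departs from the protocol without saying so.

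If the protocol is followed, the primary comparison rests on a selection made after randomization. Patients who stop, or die, before day 31 cannot qualify. Failing the rule could go with slow recovery, because Protocol 6.2.6 lists deterioration as a reason to stop. It could also go with early discharge, because Protocol 5.2 has patients take the capsules themselves at home. The direction of any bias therefore cannot be known in advance.

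Read literally, the protocol's reference to NR would also let no placebo patient qualify. That is probably a drafting slip, but it needs correcting.

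**Working it through.** **Inputs.** From Protocol 10.1 and SAP 2.3: Weibull length of stay with scale 18 and shape 2.2; maximal reduction 33%; groups of 18 placebo, 10, 10 and 20 on NR. From SAP 2.4: Step 1 compares 20 on 1 g/day with 18 on placebo, two-sided 5%. The share of patients failing the 30-day rule is not given (Protocol 10.1 says dropout is unknown), so it is assumed below.

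**1. The plan's own figures.** Weibull quantiles are 18 × (−ln(1−p))^(1/2.2), giving median 15.2 and quartiles 10.2 and 20.9, against the stated 15 and 10–21. The MCPMod power of about 80% also reproduces: 77–83% by curve, mean 79%, using the Weibull-model variance, one-sided 2.5% and assumed curve shapes (the documents give neither the MCPMod alpha nor the shapes). That calculation uses all 58 patients with no allowance for exclusions, which fits the FAS and not a subset.

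**2. When the 30-day rule can be met.** P(T ≤ 30) = 1 − exp(−(30/scale)^2.2).
- Placebo, scale 18: (30/18)^2.2 = 3.077, so 1 − 0.0461 = 95.4%.
- Stay 33% shorter, scale 18 × 0.67 = 12.06: 1 − 0.0006 = 99.9%.

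With no effect, about 58 × 0.0461 = 2.7 patients would still be in hospital after day 30. For nearly everyone else, inclusion depends on capsules taken after the endpoint. Exclusion can be settled earlier, by stopping for good or dying in hospital.

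**3. Effect on Step 1 if the protocol rule were followed, with no true effect.** Simulation of 20 v 18 patients, Weibull proportional hazards model with treatment only, Wald test, no deaths or censoring, 6,000 trials per row. HR above 1 favours NR. False-favourable means significant in favour of NR (nominal 2.5%). Failures come at random, from the slower or faster half of that arm's stays, or (extreme case) from the longest stays.

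| Failing, NR v placebo | Who fails | HR | False-favourable | Two-sided rejection |
|---|---|---|---|---|
| none (FAS) | – | 1.00 | 3.1% | 6.4% |
| 10% v 5% | slower half | 1.04 | 3.7% | 6.2% |
| 10% v 5% | faster half | 0.96 | 2.2% | 6.5% |
| 20% v 5% | random | 1.01 | 3.5% | 6.5% |
| 20% v 5% | slower half | 1.20 | 8.8% | 10.0% |
| 20% v 5% | faster half | 0.87 | 1.4% | 8.2% |
| 20% v 5% | longest stays | 1.55 | 28.0% | 29.6% |
| 5% v 20% | slower half | 0.83 | 1.4% | 11.2% |
| 5% v 20% | faster half | 1.14 | 6.6% | 8.3% |
| 20% v 20% | random | 1.00 | 3.1% | 6.3% |
| 20% v 20% | slower half | 0.99 | 4.2% | 9.2% |
| 20% v 20% | faster half | 0.99 | 3.4% | 7.5% |
| 20% v 20% | longest stays | 1.00 | 10.7% | 21.7% |

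The simulation error on a 6% rate is √(0.06 × 0.94/6,000) ≈ 0.3 percentage points. At equal failure rates of 5–10% from the slower or faster half, repeated runs gave two-sided rejection of 6.2–7.3%, against 5.7–6.4% with no exclusions. That is little or no rise.

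**4. Power lost to random failures.** The HR for a 33% reduction is 0.67^(−2.2) = 2.41. With all 38 patients, √(38 × 18/38 × 20/38) × ln 2.41 − 1.96 = 0.75, which gives 77%. Keeping 90, 80 or 70% of patients gives 73, 68 or 62%. Simulation with 0, 10, 20 and 30% failing in both arms gives 76, 72, 66 and 60%. This is the 38-patient Step 1 test, not the 58-patient MCPMod calculation.

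**The case against.** The strongest reply is that the later and more detailed document already plans the right analysis. SAP 6.1 is unambiguous, SAP 2.4 says there is a single primary analysis, and Protocol 10.4 and 10.5 point to the SAP for detail. On that view what remains is a stale protocol line, and the bias figures describe an analysis nobody intends to run. Much of this stands, and it lowers the severity. It does not remove the contradiction: the primary population is more than a detail, Protocol 10.3 states its choice twice, and neither document gives precedence.

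The failure rates are assumptions and the bar is low, at just over 30 days of a 90-day supply. Protocol 5.3 lets patients whose dosing was postponed finish their capsules, and Protocol 4.4 excludes those expected to die within 90 days. Failure rates may therefore be small, and small gaps move little.

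A reader might infer that the FAS was chosen with knowledge of the results, because SAP 5 reports that only one patient's discharge came later than medical fitness. The documents do not support that. The remark is pooled and names no arm. SAP 2.6 places lock, unblinding and analysis in the future, SAP 3.2 says metabolite results come only after unblinding, and Protocol 10.2.3 keeps the statistician blinded until lock.

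A reader might also infer that selection related to length of stay always inflates the false-positive rate, even at equal failure rates. The simulations show a clear rise only at about 20% failing, or when the longest stays are the ones that fail.

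**Conclusion.** The two documents name different primary populations, and the protocol's choice is wrong as written; this should be fixed. The FAS in SAP 6.1 is the sound choice, so the fault lies in Protocol 10.3 and in the unrecorded change, not in the analysis that the SAP plans.

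If Protocol 10.3 were followed, the null HR could move to about 1.2 or 0.87 with a 20% v 5% gap tied to length of stay, but only to about 1.04 or 0.96 with 10% v 5%. Random failures of 10–30% would cost Step 1 about 4 to 16 points of power (76% to 72–60%). These sizes rest on the planning Weibull, on assumed failure rates and on no deaths. The 95.4% and 99.9% figures rest on the planning Weibull and the 33% effect alone. The contradiction itself rests on no assumption.

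**What to change.** 1. In Protocol 10.3, delete both statements that per-protocol is primary. Name as primary the FAS of SAP 3.4, analysed by allocated group. Replace the 30-day definition with the SAP's PPS, worded as *study medication* and not NR, for sensitivity only.
2. Align Protocol 6.3.1 with this by reporting, by arm, any randomized patient who received no dose. Few are expected, because the box is handed over when the first capsule is taken (Protocol 10.2.2), and SAP 4.1 already lists patients who did not receive their allocation.
3. Add one sentence to SAP 6.1, for example: *The FAS replaces the primary population of Protocol version 1.46, section 10.3; this was decided on [date].* If the decision came after database lock, report it as a deviation in the Clinical Study Report under Protocol 10.4.

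The cost is wording in two documents, plus ethics committee approval of the protocol amendment (Protocol 11.4). If that is impractical, item 3 alone settles precedence. No analysis is added. The FAS keeps non-adherent patients and may slightly dilute a true effect; the planned PPS analysis indicates by how much.

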#### 10.4 Planned analyses

The main statistical analysis is planned when

- The planned number of patients has been included OR the required number and more are included after a period of 2 years.
- All included patients have either finalized their last assessment or has/is withdrawn according to protocol procedures
- All data have been entered, verified and validated according to the data management plan Prior to the main statistical analysis, the data base will be locked for further entering or altering of data. The treatment allocation will be revealed after the database lock and used in the statistical analysis.

Deviation from the original statistical plan will be described and justified in the Clinical Study Report. Amendments to plan can be done until day of DB lock.

#### 10.5 Statistical Analysis

Details of the statistical analyses will be described in the Statistical analysis plan (SAP). An outline of the SAP is described here.

### 10.5.1 Primary Endpoint

Length of stay from randomization to discharge from hospital

The number of days will be calculated as number of hours/24 from randomization to final discharge from hospital (to home, long term care facility or rehabilitation centre or other facility with a lower care level). Admission to other hospitals after transfer from the first will be included in the total length of stay.

#### 10.5.2 Secondary Endpoint of Special Interest:

Change in the level of frailty measured as grip strength at inclusion, on day 7, and on day 90. Should a patient withdraw from the study, grip strength will be measured at the withdrawal visit.

Grip strength is a simple measure used to indicate overall muscle strength (34, 33). It has been shown to inhabit health-related prognostic value and evidence suggests that it is a powerful predictor of future disability, falls, morbidity and mortality (33, 35-37). Grip strength will be measured in both arms using a dynamometer. Each participant will be tested twice on both the right and left, and the highest score on either side will be registered.

#### 10.5.3 Other Secondary Endpoints:

Comparing the intervention group with the placebo group with regards to the following:

- 1. Time to normalization of blood pressure and resolution of fever.
- 2. Respirator days after randomization.
- 3. Length of stay from randomization to medically fit for discharge.
- 4. 90 days, one year and very long-term mortality from randomization.
- 5. Measure NAD+ and metabolite levels BEFORE, during and after acute illness in patients using NR and placebo.
- 6. Number of new infections and re-admission during follow-up.
- 7. If significant differences in endpoints are found in the NR and placebo group, we wish to investigate the following:
  - Epigenetic mechanisms of how NR shortens recovery time after acute illness.
  - b. To identify characteristics of the patients that benefits most from NR supplementation after acute illness.
  - c. To identify the optimal NR dose yielding the largest reduction in recovery time.

See also table 3 with secondary endpoints (except variables only collected at baseline)

